10. SAFETY REPORTING

10.1 Definitions

Adverse Event (AE)

An AE or adverse experience is:

Any untoward medical occurrence in a patient or clinical investigation participants administered a medicinal product, which does not necessarily have to have a causal relationship with this treatment (the study medication).

An AE can therefore be any unfavourable and unintended sign (including an abnormal laboratory finding), symptom or disease temporally associated with the use of the study medication, whether or not considered related to the study medication.

Adverse Reaction (AR)

All untoward and unintended responses to a medicinal product related to any dose. The phrase "responses to a medicinal product" means that a causal relationship between a study medication and an AE is at least a reasonable possibility, i.e., the relationship cannot be ruled out.

All cases judged by either the reporting medically qualified professional or the Sponsor as having a reasonable suspected causal relationship to the study medication qualify as adverse reactions.

Severe Adverse Events (SAE)

To ensure no confusion or misunderstanding of the difference between the terms "serious" and "severe", which are not synonymous, the following note of clarification is provided:

The term "severe" is often used to describe the intensity (severity) of a specific event (as in mild, moderate, or severe myocardial infarction); the event itself, however, may be of relatively minor medical significance (such as severe headache). This is not the same as "serious," which is based on patient/event outcome or action criteria usually associated with events that pose a threat to a participant's life or functioning. Seriousness (not severity) serves as a guide for defining regulatory reporting obligations.

Serious Adverse Event or Serious Adverse Reaction (SAE or SAR)

A serious adverse event or reaction is any untoward medical occurrence that at any dose:

- Results in death,
- Is life-threatening,

NOTE: The term "life-threatening" in the definition of "serious" refers to an event in which the participant was at risk of death at the time of the event; it does not refer to an event which hypothetically might have caused death if it were more severe.

- Requires inpatient hospitalisation or prolongation of existing hospitalisation,
- Results in persistent or significant disability/incapacity, or
- Is a congenital anomaly/birth defect.
- Other important medical events*

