*Other events that may not result in death, are not life threatening, or do not require hospitalisation, may be considered a serious adverse event when, based upon appropriate medical judgement, the event may jeopardise the patient and may require medical or surgical intervention to prevent one of the outcomes listed above.

Expected Serious Adverse Events/Reactions (SAE)

The most common adverse events associated with Empagliflozin (Jardiance™) are urinary tract and mycotic fungal infections (e.g. balanitis) and volume depletion leading to dehydration, postural hypotension and dizziness. If these events lead to hospitalisation of the participant, they will require immediate reporting to the study team. Otherwise, they will be treated as an AE and need reporting to the study team within 2 working days.

Abnormalities of renal and liver function will also be closely monitored as part of the usual study visits and any significant clinical deterioration in renal and/or liver function will be reported as an SAE. A serious deterioration in renal function to be classified as an SAE will be a reduction in eGFR to less than 30ml/min/1.73m². A serious deterioration in liver function will be classified as an SAE if ALT or AST is 3x greater than the upper limit of normal (ULN).

Ketoacidosis and Diabetic Ketoacidosis (DKA) have recently been reported as a possible serious SAE occurring with SGLT-2 inhibitor use by the US Food and Drugs Administration. Participants will be closely monitored for the development of this SAE and will be advised to seek medical attention immediately if they experience symptoms such as difficulty breathing, nausea, vomiting, abdominal pain, confusion, unusual fatigue or sleepiness, anorexia, excessive thirst, dehydration, low food intake, weight loss, infection, poor control of diabetes, and/or only moderately increased glucose levels.

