10.3 Reporting Procedures for Serious Adverse Events

All SAEs, except those expected ones defined in Section 10.1 (pg. 35) that do not require immediate reporting will be reported to the Sponsor and Boehringer Ingelheim within 24 hours of discovery or notification of the event. The SAE will be reported using appropriate forms and the immediate report will be made in writing and shall be followed by a detailed written report of the event. Additional information can be provided if requested to the Sponsor and main Research Ethics Committee (REC) (e.g. in the event of a death). The Principal Investigator or another delegated physician is responsible for the review and sign off of the SAE, or in their absence, another member of the team (in order to avoid a delay).

The Sponsor will perform an initial check of the information and ensure that it is reviewed at the next R&D management meeting. All SAE information must be recorded on an SAE form and sent to the Sponsor. Additional information received for a case (follow-up or corrections to the original case) needs to be detailed on a new SAE form and sent to the Sponsor.

The Sponsor will report all SUSARs to the MHRA and the REC concerned. Fatal or life-threatening SUSARs must be reported within 7 days and all other SUSARs within 15 days. The Chief Investigator will inform all investigators concerned of relevant information about SUSARs that could adversely affect the safety of participants. The Sponsor will use the Summary of Product Characteristics (SmPC) as the Reference Safety Information (RSI) when determining the expectedness of any untoward medical occurrences and thus SAE/SUSAR reporting.

In addition to the expedited reporting above, the Chief Investigator will submit once a year throughout the clinical study or on request a Developmental Safety Update Report (DSUR) to the MHRA and REC. The PI will inform all investigators concerned of relevant information about SUSARs that could adversely affect the safety of participants.

The investigator site file will contain documentation for:-

- SAE, SAR and SUSAR reports
- Evidence of submission of SAEs to the Sponsor within 24 hours of the team becoming aware of an event
- Evidence of timely SUSAR submission to the MHRA and main REC.

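### For urinary and mycotic infections and volume-depletion events, Protocol 10.1 names hospitalisation as the only trigger for immediate reporting, which contradicts its own six-criterion SAE definition

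*Protocol*

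**What the plan says.** Protocol 10.1 opens its definition of seriousness broadly: "A serious adverse event or reaction is any untoward medical occurrence that at any dose" meets one of six criteria. These begin with "Results in death". They go on to life-threatening events, admission or a prolonged stay, lasting disability, congenital anomaly, and other important medical events. The last group covers cases where, on medical judgement, "the event may jeopardise the patient and may require medical or surgical intervention to prevent one of the outcomes listed above".

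A later paragraph in the same section, on expected SAEs, takes the drug's most common adverse events: "urinary tract and mycotic fungal infections (e.g. balanitis) and volume depletion leading to dehydration, postural hypotension and dizziness". It says of them: "If these events lead to hospitalisation of the participant, they will require immediate reporting to the study team". The next sentence deals with all remaining cases: "Otherwise, they will be treated as an AE and need reporting to the study team within 2 working days".

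Protocol 10.3 sets the 24-hour report to the sponsor and manufacturer. It applies to "All SAEs, except those expected ones defined in Section 10.1 (pg. 35) that do not require immediate reporting". The same section says that all SAE information must go to the sponsor on an SAE form, and it requires the site file to show that SAEs were submitted within 24 hours.

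SAP 5.5 summarises, by randomised group, the number and percentage of individuals with an adverse event or a serious adverse event. It has no step for reclassifying events.

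**The concern.** Seriousness should be judged in the same way for every event. Expectedness is a separate question, which matters when deciding whether a serious reaction is a SUSAR. The expected-event paragraph mixes the two: for a short list of event types, being expected narrows the test of whether the event is serious.

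Three uses of the data depend on that classification:

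- **The 24-hour report.** It is triggered by SAE status. An event filed as an AE goes only to the study team, in 2 working days.
- **The SUSAR assessment.** Under 10.1 it starts from a reaction already classed as serious, and asks whether its nature or severity departs from the product information. A familiar event type with an unusually severe outcome is a case that this assessment is meant to catch.
- **The by-arm safety summary in SAP 5.5.** It takes the classification as filed.

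The listed event types are ones that the protocol links to empagliflozin, so an error in classifying them need not be balanced between drug and placebo.

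**Working it through.** No formula applies; the check is a comparison of text. The inputs are the SAE criteria and the expected-event paragraph in Protocol 10.1, the reporting procedure in 10.3, and SAP 5.5.

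**Step 1. The six criteria against the rule for the listed events.**

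| Criterion | General definition (10.1) | Listed infection or volume-depletion event |
|---|---|---|
| Death | SAE | Not named, so AE |
| Life-threatening | SAE | Not named, so AE |
| Admission, or a prolonged stay | SAE | New admission: immediate report. Prolonged stay: not named |
| Lasting disability or incapacity | SAE | Not named, so AE |
| Congenital anomaly | SAE | Not named (hardly relevant in men and postmenopausal women) |
| Other important medical event | SAE if so judged medically | Not named, so AE |

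One criterion of six is kept, and only in part. Of the five left out (6 − 1), four are relevant to this population. No sentence says that the general criteria still govern the listed events.

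**Step 2. Which events are affected.** Only urinary tract infection, mycotic infection and volume depletion (dehydration, postural hypotension, dizziness). Renal and liver deterioration have their own SAE rule in 10.1. The events of special interest (decreased renal function, hepatic injury, diabetic ketoacidosis, lower limb amputation) follow the SAE procedure. None of these carries a hospitalisation test.

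**Step 3. The path of an affected event.** Take a life-threatening episode of volume depletion without a new admission, for example in someone already in hospital. Under the general definition it is an SAE and is due to the sponsor and manufacturer in 24 hours. Under the expected-event paragraph it is an AE, due to the study team in 2 working days. It then does not enter the SUSAR assessment, and where SAP 5.5 shows AEs and SAEs separately it stands in the AE column.

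**Step 4. The exemption in 10.3.** It removes from the 24-hour report those expected SAEs that 10.1 says need no immediate reporting. But 10.1 defines no such class: the listed events without hospitalisation are called AEs there, not SAEs. The clause therefore has no clear object, and it sits badly with the requirement in 10.3 itself for evidence of 24-hour submission, which has no exception.

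**Step 5. Exposure.** Protocol 11.2 plans 76 participants in four arms, 76 / 4 = 19 per arm. Two arms receive empagliflozin, so 2 × 19 = 38 take the drug. This is a count of people exposed, not of misfiled events.

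**The case against.** The strongest reply is that the general definition is never switched off. It applies to any untoward occurrence, and 10.3 says all SAE information goes to the sponsor. On this view the expected-event paragraph only sets how quickly common events reach the study team, and an investigator who follows the general definition will report correctly. This stands in part: correct reporting is possible, and a death would probably be reported whatever the paragraph says. But the paragraph also says how the remaining events are to be classified, and correct reporting should not depend on staff setting aside an explicit instruction.

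Other points limit the consequences:

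- Protocol 11.4 has the monitoring committee see adverse and serious adverse events unblinded, so a misfiled event is not hidden. Its routine reviews are six-monthly (16.2), which does not replace a 24-hour report.
- Every AE is recorded with its severity and relatedness (10.2). If SAP 5.5 is read as one combined count, the individual is counted either way.
- Most of these reactions are expected, so only an atypically severe one could be lost to the SUSAR assessment.
- The important-medical-event criterion depends on medical judgement, so an infection treated without admission is not automatically an SAE. An injury from a fall is not on the list and can be judged as an event in its own right.
- The protocol's background section describes the infections as generally mild. Few events may be affected.

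Two stronger readings are tempting. A reader might infer that the 10.3 exemption releases ketoacidosis, or renal and liver deterioration, from expedited reporting, since they stand under the same heading. The documents do not support this: 10.1 nowhere says that these need no immediate reporting, it calls renal and liver deterioration SAEs, and it sends ketoacidosis through the SAE procedure. A reader might also infer that SAEs are in fact under-recorded in the empagliflozin arms. That cannot be shown: the documents give no event rates, the rule is the same in all arms, and drug allocation is blinded.

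**Conclusion.** Protocol 10.1 contradicts itself on seriousness for three event types: urinary tract infection, mycotic infection and volume depletion. For these, a literal reading keeps one of six criteria, and that one in part. The consequence rests on one assumption: that a site follows the expected-event paragraph as written instead of the general definition. The affected events are those serious without a new admission, and their number cannot be estimated from the documents. If there are any, the SAE count could be too low, possibly more so among the 38 participants planned for empagliflozin; that direction is an inference from the drug's known effects. The exemption in 10.3 is unclear, not plainly harmful. The primary outcome, its analysis and the error rates are untouched. The point is still worth correcting, because it bears on expedited safety reporting and costs little.

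**What to change.** 1. In Protocol 10.1, change the trigger for the listed events from hospitalisation to meeting any of the seriousness criteria given earlier in that section. The AE route with 2 working days then applies only to events that meet none of them.
2. In Protocol 10.3, delete the exemption from the 24-hour report. It refers to a class that 10.1 does not define, and the site-file requirement already assumes 24-hour submission of SAEs.
3. State that expectedness, judged against the product information as 10.3 already provides, is used only for the SUSAR decision and not to separate an SAE from an AE.
4. Before the SAP 5.5 summary is produced, check any AEs of these types already filed against all six criteria, without sight of the drug allocation, and correct the classification where needed.

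The cost is a short protocol amendment, one review of filed AEs of three types, and possibly a few more SAE forms. No visit, measurement or efficacy analysis changes.

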10.2 Reporting Procedures for All Adverse Events

All AEs, including AESI, occurring during the study observed by the investigator or reported by the participant, whether or not attributed to study medication, will be recorded on the CRF and medical records.

The following information will be recorded: description, date of onset and end date, severity, assessment of relatedness to study medication, other suspect drug or device and action taken. Follow-up information should be provided as necessary.

AEs considered related to the study medication as judged by a medically qualified investigator or the Sponsor will be followed until resolution or the event is considered stable. All related AEs that result in a participant's withdrawal from the study or are present at the end of the study, should be followed up until a satisfactory resolution occurs. The duration of safety follow-ups will be at least five half-lives of the study medication. The half-life of Empagliflozin (Jardiance™) is 12.4 hours, thus the duration of safety follow-ups will be rounded up to be at least 72 hours (or 3 days).

It will be the investigator's clinical judgment whether or not an AE is of sufficient severity to require the participant's removal from treatment (see Section 8.9, pg. 30).

A participant may also voluntarily withdraw from treatment due to what he or she perceives as an intolerable AE. If either of these occurs, the participant must undergo an end of study assessment and be given appropriate care under medical supervision until symptoms cease or the condition becomes stable. The duration of safety follow-ups will be at least five half-lives of the study medication. The half-life of

Empagliflozin (Jardiance[™]) is 12.4 hours, thus the duration of safety follow-ups will be rounded up to be at least 72 hours (or 3 days).

The severity of events will be assessed on the following scale: 1 = mild, 2 = moderate, 3 = severe.

The relationship of AEs to the study medication will be assessed by a medically qualified investigator.

10.3 Reporting Procedures for Serious Adverse Events

All SAEs, except those expected ones defined in Section 10.1 (pg. 35) that do not require immediate reporting will be reported to the Sponsor and Boehringer Ingelheim within 24 hours of discovery or notification of the event. The SAE will be reported using appropriate forms and the immediate report will be made in writing and shall be followed by a detailed written report of the event. Additional information can be provided if requested to the Sponsor and main Research Ethics Committee (REC) (e.g. in the event of a death). The Principal Investigator or another delegated physician is responsible for the review and sign off of the SAE, or in their absence, another member of the team (in order to avoid a delay).

The Sponsor will perform an initial check of the information and ensure that it is reviewed at the next R&D management meeting. All SAE information must be recorded on an SAE form and sent to the Sponsor. Additional information received for a case (follow-up or corrections to the original case) needs to be detailed on a new SAE form and sent to the Sponsor.

The Sponsor will report all SUSARs to the MHRA and the REC concerned. Fatal or life-threatening SUSARs must be reported within 7 days and all other SUSARs within 15 days. The Chief Investigator will inform all investigators concerned of relevant information about SUSARs that could adversely affect the safety of participants. The Sponsor will use the Summary of Product Characteristics (SmPC) as the Reference Safety Information (RSI) when determining the expectedness of any untoward medical occurrences and thus SAE/SUSAR reporting.

In addition to the expedited reporting above, the Chief Investigator will submit once a year throughout the clinical study or on request a Developmental Safety Update Report (DSUR) to the MHRA and REC. The PI will inform all investigators concerned of relevant information about SUSARs that could adversely affect the safety of participants.

The investigator site file will contain documentation for:-

- SAE, SAR and SUSAR reports
- Evidence of submission of SAEs to the Sponsor within 24 hours of the team becoming aware of an event
- Evidence of timely SUSAR submission to the MHRA and main REC.

11. STATISTICS

11.1 Description of Statistical Methods

Participants recruited to the study will be compared within and by treatment group. For the latter, each active treatment arm, whether medication, medication and energy restriction diet or placebo and energy restriction diet, will be compared against the placebo only arm. Baseline variables will be presented by arm using N (%) for categorical variables and mean (standard deviation) or median (interquartile range) as appropriate, for continuous variables.

The primary outcome is change in appetite hormones from baseline to week 24 within and between treatment groups. AUC values for appetite hormone measurements at baseline and 24 weeks will be calculated using the trapezoidal rule. Paired t-tests or equivalent non-parametric tests will be used to analyse the change in appetite hormones within individual treatment groups. One way analysis of variance will be used to calculate mean changes in AUC from baseline to 24 weeks by treatment group. Adjusted treatment effects will be calculated via linear regression analysis or similarly appropriate methods, to compare each treatment against placebo. Models will include a categorical treatment variable and will be adjusted for stratification factors; age and BMI as well as baseline AUC value. Changes in appetite hormones from baseline to weeks 2, 6 and 12 will also be analysed using the same methods; however will represent hypothesis generating analyses only. Similarly, overall changes in appetite hormones over time will be analysed using multilevel models, adjusted for stratification factors.

The analysis for the primary outcome will be repeated for secondary endpoints; changes in resting energy expenditure, weight and body composition, physical activity and biochemical parameters from baseline.

All analyses of outcome data will be carried out on a complete case basis, so only those patients with complete data will be included in the analysis. Intention to treat and per protocol analyses will be carried out as sensitivity analyses, using multiple imputation and including only those who remain on their treatment regimen for the duration of the study, respectively.

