8.10 Discontinuation/Withdrawal of Participants from Study Treatment

Each participant has the right to withdraw from the study at any time without needing to give a reason. In addition, the Investigator may discontinue a participant from the study at any time if the Investigator considers it necessary for any reason including:-

- Participant intolerance to study medication, as assessed at each visit by the study team, will necessitate withdrawal of participant from the study as study drug dose will not be reduced during the trial
- Ineligibility (either arising during the study or retrospective having been overlooked at screening)
- Significant protocol deviation
- Significant non-compliance with treatment regimen or study requirements
- An adverse event which requires discontinuation of the study medication or results in inability to continue to comply with study procedures
- Disease progression which requires discontinuation of the study medication or results in inability to continue to comply with study procedures
- Consent withdrawn
- Lost to follow up

The reason for withdrawal will be recorded in the CRF and medical records if known. If the participant is withdrawn due to an adverse event, the investigator will arrange for safety follow-up visits or telephone calls until the adverse event has resolved or stabilised. The duration of safety follow-ups will be at least five half-lives of the study medication. The half-life of Empagliflozin (Jardiance™) is 12.4 hours, thus the duration of safety follow-ups will be rounded up to be at least 72 hours (or 3 days).

The participant will be withdrawn from the study if they lose capacity and data collected up to that point will be used for analysis. As analysis will be on an intention-to-treat basis, there will be analysis of all data of participants receiving study medication (e.g. most safety analyses) and data will be admitted to the database even after the participant has withdrawn from the study.

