11.2 The Number of Participants

The power calculation is based on the primary outcome of change in appetite hormones and a standard deviation of AUC of 96.2pg/ml of total PYY based on a study looking at the influence of resistance and aerobic exercise on hunger and circulating levels of total PYY in healthy males (Broom 2009). To detect a minimum clinically significant difference of 120pg/ml in AUC of total PYY between groups, we will require 15 participants in each of the four arms with 80% power and 2-sided alpha of 1.7%. This will allow three comparisons between arms. To account for up to 20% dropout, 19 participants will be required in each arm; therefore 76 participants will be recruited in total.

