5.3.3 Secondary outcomes

PYY time averaged AUC responses at weeks 2, 6 and 12 will also be analysed using the same methods as above. For summary purposes, Generalised Estimating Equations (GEE) taking account of repeated measures (2, 6, 12 and 24 weeks) with an exchangeable correlation matrix adjusted for baseline value and stratification variables (Age & BMI) will be used to derive an average PYY AUC response across time for each of the intervention groups compared to the control group, with significance assigned using the same method as that described for the primary outcome. Objective physical activity measures will be adjusted for ActiGraph wear time at baseline and follow up.

All other secondary outcomes will be analysed using the same approach as that described for the primary outcome. Models of ActiGraph measured outcomes will additionally be adjusted for ActiGraph wear time at baseline and follow-up.

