5.4.3 Multiple imputation

An additional sensitivity analysis of the primary outcome will be performed using multiple imputation which substitutes predicted values from a regression equation assuming Missing At Random. This will be carried out where AUC values are reported as missing based on the above criteria. The imputation will be carried out by the MI command in Stata ⁴. MI replaces missing values with multiple sets of simulated values to complete the data, performs standard analysis on each completed dataset, and adjusts the obtained parameter estimates for missing-data uncertainty using Rubin's rules to combine estimates ⁵.

The following procedure will be followed:

- Multiple imputation will be carried out by chained equations to impute the entire PYY AUC values, using the variables PYY AUC, treatment group, baseline value and the stratification variables.
- The MI will be set as wide
- A regression method will be used, where the registered variables will be individually adjusted for the randomisation and stratification factors (BMI and age), with 100 imputations to avoid biased estimates, seed (2259) and the force options
- MI estimate will provide the final results using the same regression model as the primary analysis and covariate adjustments.

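### The week-24 PYY contrast makes no use of week 2, 6 and 12 curves from participants without a week-24 curve, and can be biased if dropout follows post-baseline PYY

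*Protocol*

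**What the plan says.** Protocol 11.1: "All analyses of outcome data will be carried out on a complete case basis, so only those patients with complete data will be included". Protocol 11.7 and SAP 3.2.1 say the same of the main analysis. The SAP 5.3.1 model has the week-24 time-averaged AUC as its outcome, with arm, baseline PYY and the age and BMI strata as its only terms.

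Three other analyses bear on missing week-24 data or on the earlier visits:

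- SAP 5.4.2 fits a GEE to the repeated samples taken within the week-24 visit.
- SAP 5.4.3 imputes missing AUCs, using "predicted values from a regression equation assuming Missing At Random". Its inputs are PYY AUC (no visit stated), arm, baseline value and strata.
- SAP 5.3.3 fits a GEE over weeks 2, 6, 12 and 24 that "will be used to derive an average PYY AUC response across time for each of the intervention groups". Protocol 11.1 foresees multilevel models of overall change over time.

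On the analysis basis, Protocol 8.10 says analysis will be by intention to treat and that "there will be analysis of all data of participants receiving study medication"; the sentence goes on to give safety analyses as its example. Protocol 11.1 and 11.7 make intention to treat a sensitivity analysis, done by multiple imputation.

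**The concern.** Someone who withdraws after week 12 may already have given three full seven-sample PYY curves after baseline. These are the best available predictors of the missing week-24 value, and the primary contrast ignores them.

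The loss need not be even across arms. Protocol 8.10 makes intolerance of study medication a ground for withdrawal, and 9.5 does the same for a need for excluded medication. The first plausibly acts more on drug, the second more on placebo. No week-24 curve is planned after withdrawal. The end-of-study assessment that 10.2 requires after an adverse-event withdrawal is not described as one.

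The complete-case model is valid if missingness depends only on the terms in it: arm, baseline PYY and strata. If missingness also depends on PYY at weeks 2 to 12, completers differ from dropouts at week 24 even at equal baseline, and the between-arm contrast can shift.

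**Working it through.** **1. The plan's own figure.** Inputs from Protocol 11.2: SD 96.2 pg/ml, difference sought 120 pg/ml, dropout 20%, and the statement "we will require 15 participants in each of the four arms with 80% power and 2-sided alpha of 1.7" (per cent).

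- Normal approximation: n = 2(z₁₋α/₂ + z₀.₈)²(SD/δ)² = 2 × (2.387 + 0.842)² × (96.2/120)² = 2 × 10.42 × 0.643 = 13.4, so 14 per arm.
- Noncentral t: power is 76.8% at 14 and 80.3% at 15, so 15 per arm.
- Dropout: 15/0.8 = 18.75, so 19 per arm, and 4 × 19 = 76.

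The sample size reproduces, and the plan allows for losing about 4 of 19 per arm. For scale, the standard error of one contrast is 96.2 × √(2/15) = 35.1 pg/ml, before any gain from covariates.

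**2. Which analyses let earlier curves inform week 24?**

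| Analysis | Uses weeks 2, 6, 12? | Estimates the week-24 contrast? |
|---|---|---|
| SAP 5.3.1 main model | No | Yes |
| SAP 5.4.2 GEE | No | Yes |
| SAP 5.4.3 imputation | Not named | Yes |
| SAP 5.3.3 GEE | Yes | No, average over visits |
| Per-visit models (Protocol 11.1, SAP 5.3.3) | Yes | No, each at its own visit |

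No row clearly has both.

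**3. Possible bias, large-sample simulation.** From the documents: SD 96.2, effect 0 or 120, 20% overall dropout. Assumed, because the documents give nothing: dropout after week 12; log-odds slope of 1 to 2 per SD of week-12 PYY; between-visit correlation AR(1) 0.5 to 0.85, or exchangeable 0.3 to 0.8 (slope 1 only). There were 200,000 participants per arm. Bias is the estimate minus the true effect. The complete-case model is Y₂₄ on arm and Y₀ in completers. The comparison predicts missing Y₂₄ from arm, Y₀, Y₂, Y₆ and Y₁₂, then refits.

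| Assumed dropout | Complete-case bias (pg/ml) |
|---|---|
| Random, or on baseline PYY only (exchangeable runs) | about 0 |
| On week-12 PYY, same rule in both arms, no effect | about 0 |
| Same rule, effect 120 | −2 to −17 |
| On PYY in the active arm only, low values lost | +1.5 to +20 |
| Opposite directions by arm | −5 to −32 |

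With the three visits included, bias was within 1 pg/ml in every run. Imputing from arm and baseline alone, as the SAP 5.4.3 list reads, gave the same bias as complete case (exchangeable runs).

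Example: AR(1) 0.7, slope 1, effect 120, opposite directions, with dropout 28% on drug and 12% on placebo. The complete-case bias is −21.1, so the estimate is 120 − 21.1 = 98.9. With the visits included it is 120 − 0.5 = 119.5. The largest value, −31.9, came with slope 2 and no effect. It is 31.9/35.1 = 0.91 of a standard error.

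**4. Main scenario at trial size.** 19 per arm; effect path 15/45/80/120 or zero; correlation AR 0.6/0.75/0.85 or exchangeable 0.6; dropout about 25 to 31% on drug and 12% elsewhere; log-odds +1 per SD of the last observed PYY in the drug arms only.

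- Complete-case bias was about −4 to −12; one set of runs at effect 120 reached −15. The repeated-measures estimate was within 2 of the truth. Twelve is 12/120 = 10% of the target and 12/35.1 = 0.34 of a standard error.
- Root mean squared error, complete case against repeated measures: 28.8–35.0 against 28.3–34.0 (effect 0), and 30.2–37.7 against 29.0–36.2 (effect 120).
- Complete-case rejection at nominal 1.7% was 1.4 to 2.6% across runs. The Monte Carlo error with 2,500 trials is √(0.017 × 0.983/2500) = 0.26 points.
- With 20% dropout unrelated to PYY there is no bias, and the repeated-measures model lowers variance by 4 to 8%.

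**The case against.** **The plan does address missing data.** It has multiple imputation, a GEE that keeps anyone with a single week-24 sample, and a rule keeping curves with at least 4 of 7 samples (SAP 5.4.1). This stands. "PYY AUC" in SAP 5.4.3 carries no visit label, so the earlier AUCs may be intended. If they are, the imputation closes the gap as a sensitivity analysis, but the text does not say so.

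**Nothing in the documents ties withdrawal to PYY.** Also true. The size and even the sign of the bias follow from the mechanism chosen: losing low values on drug pushes the estimate up, losing high values pushes it down.

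**The gain is small at this sample size.** Root mean squared error barely moves. No rejection rate is available for the repeated-measures model, so no improvement in type I error is shown. The simulations used regression-based estimates, not the Kenward-Roger fit proposed below.

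**Protocol 8.10 may not be contradicted.** A reader might infer that it promises every early curve a place in the week-24 contrast. It does not. The sentence about data collected up to withdrawal concerns loss of capacity, the one about all data gives safety analyses as its example, and the early curves are used in secondary analyses. What remains is narrower: intention to treat is the basis in 8.10 and a sensitivity analysis in 11.1 and 11.7.

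**Conclusion.** The point holds in a conditional form. As written, no analysis clearly lets a withdrawn participant's week 2, 6 and 12 curves inform the week-24 contrast. The contrast can be biased if dropout depends on post-baseline PYY and the mechanism differs by arm, or if there is a treatment effect. Under the assumptions tried, the absolute bias was 0 to about 32 pg/ml, and about 4 to 12 in the main scenario, against a target of 120 and a standard error of about 35.

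A reader might go further and conclude that the primary result is biased. The documents do not support that. Bias is about nil when dropout is random, when it depends only on baseline PYY (already adjusted for), or when the same rule acts in all arms and there is no effect. Nor is the repeated-measures model unconditionally unbiased: it needs missing at random and a correct mean model, and dropout driven by the unseen week-24 value would bias it too. Its advantage is that it allows dropout to depend on the observed follow-up PYY, which the complete-case model does not.

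**What to change.** - Estimate the three week-24 placebo contrasts from a repeated-measures linear model on the PYY AUCs at weeks 2, 6, 12 and 24, with arm-by-visit, baseline AUC-by-visit, strata, unstructured covariance and Kenward-Roger degrees of freedom. Keep the Holm rule of SAP 5.3.2, and keep the complete-case model as a sensitivity analysis. The same fit can serve the over-time analysis in Protocol 11.1.
- At minimum, name the week 2, 6 and 12 AUCs as inputs to the SAP 5.4.3 imputation model, and state which visit each PYY AUC refers to.
- Reconcile the intention-to-treat statement in Protocol 8.10 with 11.1 and 11.7.

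The cost is wording and one standard model. No new data are needed, and the sample size stays at 15 evaluable and 19 recruited per arm, 76 in total. The downside is a slightly more complex model: four visits give 4 × 5/2 = 10 covariance parameters.
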